8 STATISTICAL CONSIDERATIONS

This study is a two-center, double-blind, randomized, placebo-controlled phase 1/2 clinical trial in which the safety and tolerability of tofacitinib will be assessed in patients with early dcSSc, preliminary efficacy (activity) will be estimated, and exploratory mechanistic research assessments will be performed. Fifteen subjects will be enrolled into the trial, which involves a 24-week course of 5 mg BID tofacitinib or placebo, followed by a 24-week open-label extension period of 5 mg BID tofacitinib.

This section describes the planned analyses; however, a statistical analysis plan (SAP) will be written that provides detailed descriptions of the analyses to be conducted. The SAP will be finalized prior to unblinding of the data.

Continuous variables will be summarized using descriptive statistics including n, mean, median, standard deviation, range (e.g., minimum and maximum). Qualitative variables will be

summarized using counts and percentages. Summaries will be provided by treatment group and overall. Unless otherwise specified, statistical analyses will be performed using SAS Version 9 or higher. Where appropriate, statistical tests will be conducted at the 0.1 significance level using two-tailed tests and p-values will be reported. Given the study objectives and size of this study, the statistical power of any comparisons is limited and p-values will be interpreted as hypothesis generating and not definitive. No adjustment for multiplicity will be made.

8.1 Sample Size Considerations

The planned sample size of 15 evaluable early dcScC subjects is based on practical considerations, rather than a desired power to detect for a pre-specified treatment difference. With the proposed sample of 15 subjects for the primary efficacy analyses (10 tofacitinib and 5 placebo), there would be 80% power to detect large treatment differences. For example, with a two-sided Type I error of 10% with the planned sample size, there is at least 80% power to detect a treatment difference differences in the proportion of participants who experience a Grade 3 or higher adverse event of 20% vs 86%, 10% vs 79%, or 5% vs 74% (placebo vs tofacitinib, respectively). For continuous efficacy (activity) outcomes, the proposed sample size provides 80% power (with a two-sided 10% Type I error) to detect an effect size of 1.37, or greater.

8.2 Statistical Analyses

8.2.1 Safety Outcomes

All safety analyses will be performed on the Safety Population, defined as all subjects who were randomized and received at least one dose of the study drug. Subjects will be analyzed by the treatment received.

Safety measures including AEs, clinical laboratory tests, vital signs, ECG, physical exams, and concomitant medication usage will be summarized descriptively. For quantitative variables, descriptive statistics including number of observations, mean, median, standard deviation and range will be given for the values themselves as well as for change from baseline by treatment group at each study visit. Qualitative variables will be summarized using counts and percentages by treatment group at each study visit.

The primary endpoint is the proportion of participants who experience a Grade 3 or higher adverse event at or before Week 24 and will be compared between the two treatment groups using an exact Fisher's exact test. Exact 90% confidence intervals will be calculated to estimate the incidence of the adverse events (both primary and secondary endpoints) for each treatment group. Similar methods will be used for the secondary safety endpoints. Treatment comparisons for quantitative safety outcomes will be made using two-sample t-tests or their nonparametric counterparts (e.g., Wilcoxon rank sum test). The number (counts) of adverse events will also be compared between treatments for select adverse events (e.g., Grade 3 or higher adverse events at or before Week 24, adverse events of special interest).

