	8.2.2 Efficacy (Activity) and Exploratory Outcomes.....	34
9	STUDY MANAGEMENT	35
9.1	Compliance with protocol.....	35
9.2	Record Retention.....	35
9.3	Study Drug Record	36
9.4	Study Drug Destruction.....	36
9.5	Study Monitoring.....	36
10	RESEARCH OF HUMAN SPECIMENS, SAMPLES OR DATA.....	37
10.1	Use of Stored Samples and Data	37
10.2	Disposition of Stored Samples and Data	37
11	REFERENCES	37

Study Synopsis

Protocol Title:	Evaluation of tofacitinib in early diffuse cutaneous systemic sclerosis (dcSSc): A phase I/II two center safety and tolerability study
Clinical Phase:	Phase I/II
Sponsor:	This is a Clinical and Research Collaborative study and [name], MS will be the sponsor. Pfizer will be supplying the drug/placebo and study funding (including drug distribution at 2 sites).
Accrual Objective:	15 subjects (10 active, 5 placebo)
Accrual Rate:	Enroll over 12 month time period
Study Duration:	Up to 65-day screening period, 24 weeks of double blind follow up, followed by 24 weeks of open label, with a 30 day follow up telephone call after permanent discontinuation of medication.
Research Centers:	2: University of Michigan and University of Pittsburgh
Research Hypothesis:	Tofacitinib is safe and is well-tolerated in patients with early dcSSc
Study Schema:	5 mg BID of tofacitinib vs placebo for 24 weeks with an open label extension receiving tofacitinib 5mg, BID for 24 weeks.
Primary Outcome:	
Primary Outcome Measure:	The primary endpoint will be the proportion of participants who experience Grade 3 or higher adverse events that occur at or before Week 24.
Secondary Outcomes:	
 • To assess the efficacy of tofacitinib in improving skin thickness in early dcSSc • To assess the efficacy of tofacitinib in improving skin and peripheral whole blood biomarkers in early dcSSc • To correlate skin and peripheral whole blood biomarkers with clinical efficacy assessments

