4. INVESTIGATIONAL PLAN

4.1 Study Design and Duration

This is a phase I/II placebo controlled study to evaluate the efficacy, safety, and tolerability, and pharmacokinetics of tofacitinib as a treatment for early dcSSc. The study will enroll approximately 15 Subjects from 18 to 70 [inclusive] years of age with active dcSSc. Subjects will be randomized to tofacitinib vs. placebo in a 2:1 ratio at 5 mg twice a day for 24 weeks. Subjects will be able to continue into the open label phase during which they will receive tofacitinib 5 mg twice a day for 24 weeks. There will be also be a follow up phone call which will occur 30 days post completing/discontinuing study medication. This study will be conducted over a period of approximately 2 years. Two sites are expected to participate in this study.

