3.1.1. Subject Characteristics and Study Conduct

Table 1: TOFA Subject Disposition. All Subjects

Status	Tofacitinib N (%)	Placebo N (%)
ITT Population [1]		
Safety Population [2]		
Open Label Population [3]		
Completed Study Treatment		
Discontinued Study Early		
Reason for Discontinuation		
Subject was determined to be ineligible		
Subject withdrew consent		
Investigator withdrew subject		
Study terminated by Sponsor		
Death		
Lost to follow-up		
Other		
Permanently Discontinued Study Treatment		
Reason for Discontinuation of Study Treatment		
Adverse Event		

Note: Percentages are based on the number of subjects in the Safety Population.

- [1] The ITT population includes all patients randomized to TOFA.
- [2] The Safety Population includes all randomized subjects who received at least one dose of study medication.
- [3] The Open Label Population includes all patients in the Safety Population that have completed 24 weeks (168 Days) of Double-Blind study treatment and not withdrawn from the study.

Data cutoff date: DDMMYY

Listing 1: TOFA Early Termination. ITT Subjects.

Subject ID	Treatment	Reason for Discontinuation	Time on Treatment (Days)	Time in Study (Days)

Conditional Note: No patients have discontinued as of the data cutoff date.

Table 2: TOFA Demographic Characteristics. ITT Population

Variable Statistic or Category	Tofacitinib N=10	Placebo N=5
Age (Years)		
N		
Mean		
SD		

	Tofacitinib	Placebo
Variable Statistic or Category	N=10	N=5
Median	11 20	11 0
Min, Max		
Age, n (%)		
18 to 35 years		
>35 to 55 years		
>55 to 70 years		
Gender, n (%)		
Male		
Female		
Of Childbearing Age		
Not of Childbearing Age		
Hysterectomy		
Tubal Ligation		
Post Menopausal		
Other Reason		
Ethnicity, n (%)		
Hispanic or Latino		
Not Hispanic or Latino		
Race, n (%) [1]		
American Indian or Alaska Native		
Asian		

Variable Statistic or Category	Tofacitinib N=10	Placebo N=5
Black or African-American		
Native Hawaiian or Other Pacific Islander		
White		
Not Reported		
Smoking History, n (%) [1]		
Never		
Past History		
Current Smoker		
No Response		

Note: Percentages are 100*n/N

[1] Subjects reporting more than one race are counted in each of the race categories reported.

Table 3: TOFA Baseline Characteristics. ITT Population

Variable Statistic or Category	Tofacitinib N = 10	Placebo N = 5
mRss at Baseline		
N		

Variable Statistic or Category	Tofacitinib N = 10	Placebo N = 5
Mean		
SD		
Median		
Min, Max		

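### Tofacitinib adverse-event incidence rests on the 10 randomized subjects; former placebo subjects' first 24 weeks on open-label drug are never credited to it

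*Protocol*

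**What the plan says.** Protocol section 4.1 sets the blinded phase: "Subjects will be randomized to tofacitinib vs. placebo in a 2:1 ratio at 5 mg twice a day for 24 weeks". Those who go on enter an open-label phase "during which they will receive tofacitinib 5 mg twice a day for 24 weeks". Dose and length are therefore the same in both phases. The synopsis says the open-label phase is offered to subjects; neither document gives an expected uptake.

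For incidence, Protocol section 8.2.1 says: "Exact 90% confidence intervals will be calculated to estimate the incidence of the adverse events (both primary and secondary endpoints) for each treatment group". The same section attributes subjects in the Safety Population by the treatment they received. SAP section 2.2 names the Clopper-Pearson method at 90% and gives 10 and 5 as the largest numbers that can be affected in the two arms.

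SAP sections 2.3.1 and 2.3.2 repeat the comparison cumulatively to Weeks 36 and 48, counted from the start of study treatment and still set out as tofacitinib against placebo. Tables 17-20, 25-28 and 31-32 keep column headings of N=10 and N=5.

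SAP section 3.1.1, Table 1, defines a further group: "The Open Label Population includes all patients in the Safety Population that have completed 24 weeks (168 Days) of Double-Blind study treatment", excluding those who have withdrawn. No safety analysis uses this population. The notes to Listings 3 and 5 treat events starting on Day 169 or later as open label.

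**The concern.** The research hypothesis is that tofacitinib is safe and well tolerated in early dcSSc. Much of that question is how often severe events occur on the drug. The randomized comparison can say little unless the arms differ enormously, so the one-arm estimate on tofacitinib carries much of the safety message, and it comes from 10 subjects.

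Up to five more subjects will have a first 24-week course of the same dose. If their on-drug events are never counted as tofacitinib events, the estimate closest to the hypothesis is less precise than it could be, and an uncommon severe event is less likely to be seen under the right heading. The cumulative Week 36 and Week 48 tables make this worse, because an event that begins on open-label tofacitinib is shown as a placebo event.

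**Working it through.** **Inputs.** 10 tofacitinib and 5 placebo subjects (Protocol synopsis and section 8.1). Both phases last 24 weeks at 5 mg twice daily (section 4.1). Tests are two-sided at 0.10 (section 8) and intervals are Clopper-Pearson 90% (SAP 2.2). The number of placebo subjects who continue, k, is not given, so all values from 0 to 5 are shown.

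**1. The plan's own figure.** Section 8.1 claims at least 80% power for 20% vs 86%, 10% vs 79% and 5% vs 74%. Enumerating every outcome of a two-sided Fisher test with n = 5 and 10 gives 80.2%, 80.5% and 81.0%. The statement reproduces. It shows how large a difference the randomized comparison needs.

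**2. Event collection.** The schedule in Protocol section 6.1 marks adverse events at Weeks 6, 12, 18 (phone) and 24, then at Weeks 30, 36, 42 (phone) and 48. Subtracting 24 from the second set gives 6, 12, 18 and 24, the same spacing. CBC and comprehensive panel fall at 6, 12 and 24 weeks in each phase. Lipids do not match: they are drawn at Week 6 in the blinded phase and at Weeks 30 and 36 in the open-label phase, with none at Week 24.

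**3. Exposure if everyone completes.**
- First 24 weeks on drug: 10×24 + 5×24 = 240 + 120 = 360 person-weeks. Former placebo share: 120/360 = 33.3%.
- All planned tofacitinib exposure: 10×48 + 5×24 = 480 + 120 = 600 person-weeks. Former placebo share: 120/600 = 20%.

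**4. Precision and detection, with n = 10 + k.** With zero events the upper exact 90% limit is 1 − 0.05^(1/n). The chance of at least one event at true risk p is 1 − (1 − p)^n. The all-exposure share is 24k/(480 + 24k).

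| k | n | Share of first-24-week exposure | Share of all planned exposure | Upper limit, 0 events | At least one event, p = 10% | At least one event, p = 5% |
|---|---|---|---|---|---|---|
| 0 | 10 | 0% | 0% | 25.9% | 65.1% | 40.1% |
| 1 | 11 | 9.1% | 4.8% | 23.8% | 68.6% | 43.1% |
| 2 | 12 | 16.7% | 9.1% | 22.1% | 71.8% | 46.0% |
| 3 | 13 | 23.1% | 13.0% | 20.6% | 74.6% | 48.7% |
| 4 | 14 | 28.6% | 16.7% | 19.3% | 77.1% | 51.2% |
| 5 | 15 | 33.3% | 20.0% | 18.1% | 79.4% | 53.7% |

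**5. A non-zero case.** The limits are the 5th percentile of Beta(x, n − x + 1) and the 95th percentile of Beta(x + 1, n − x). At an observed 20%, 2/10 gives 3.7% to 50.7% and 3/15 gives 5.7% to 44.0%.

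**6. Where the events go now.** Listings 3 and 5 show them by subject. In the Week 36 and Week 48 tables the denominators stay at 10 and 5, so a former placebo subject's on-drug event falls under placebo. Tables 8-12 have no time window and the same two columns, so any open-label events included there would fall under placebo as well. No output starts the clock at the first tofacitinib dose.

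**The case against.** The strongest reply is that the blinded, randomized Week 24 comparison is the clean evidence, and that declining to pool unblinded follow-up with it is a defensible choice. The two sources are not exchangeable: the Open Label Population contains only subjects who completed 24 blinded weeks and did not withdraw, and their events are reported with the drug known. That stands. It is why a combined estimate can only be supportive, and why the narrower interval rests on an assumed common risk.

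The laboratory events of special interest raise a further difficulty. Protocol section 7.5.1 defines them against screening, which for a former placebo subject lies at least 24 weeks before the first tofacitinib dose. Changes on placebo would then count as changes on drug. Lipid events also have one on-treatment draw in the blinded phase and two in the open-label phase. Both objections stand and restrict what the table can contain.

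It can also be said that attributing the Week 36 and Week 48 events by treatment received would recover most of the content. That is only partly so: it would correct the column, but it would not give the incidence over a first 24 weeks on drug.

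Lastly, the documents set no acceptability threshold, so no stated decision would change. That is true and limits the weight of the point.

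**Conclusion.** The point holds. Every planned tofacitinib incidence estimate uses the 10 subjects randomized to it, and the on-drug events of former placebo subjects are never credited to tofacitinib. The placement in the Week 36 and Week 48 tables conflicts with the protocol's own attribution rule. The gain from correcting this is moderate and depends on uptake; with no placebo subject continuing there is none. The figures for five continuing are the best case, and they assume completed follow-up and one common risk in the two sources.

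Three stronger readings are tempting and are not supported:
- **A third of the drug exposure is lost.** One third applies only to first-24-week exposure with all five continuing. Of all planned exposure the share is at most 20%.
- **The data go unused.** They are listed and are counted at Weeks 36 and 48, but under the wrong treatment.
- **The primary analysis is at fault.** It stops at Week 24, before any placebo subject is due to start open-label drug, and is unaffected.

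This is an inexpensive improvement to the estimate nearest the hypothesis, not a flaw in the primary test.

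**What to change.** Add one descriptive table to the SAP, marked supportive: the proportion of subjects with a Grade 3 or higher adverse event, and with a Grade 2 or higher adverse event, in the first 24 weeks on tofacitinib, with Clopper-Pearson 90% intervals.

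- Set time zero at each subject's first tofacitinib dose. For former placebo subjects, use the actual open-label start rather than the assumed Day 169, because visits have a window of ±10 days.
- Show randomized tofacitinib subjects, former placebo subjects, and then the two combined. State how many placebo subjects continued.
- Include laboratory events of special interest only with the last value before the first tofacitinib dose as reference. For blood counts and the comprehensive panel in former placebo subjects, that is the Week 24 draw.
- Footnote or omit the lipid event: draw times differ by phase, and the last scheduled draw before open-label dosing is at Week 6.
- Say in the table that the open-label data are unblinded, come only from subjects who completed 24 blinded weeks, and that the combined interval assumes a common risk.
- Leave the randomized Week 24 Fisher comparison as primary.

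The cost is one table. It needs no new data and no further hypothesis test. The risk is that readers take the combined interval as randomized evidence, which the separate columns and the label are there to prevent.

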8.2.2 Efficacy (Activity) and Exploratory Outcomes

The main population for efficacy and exploratory will be the modified intention-to-treat population (MITT), defined as all subjects randomized, receiving at least one dose of treatment, and having at least one post-baseline efficacy assessment. Subjects will be analyzed by assigned treatment. No adjustment for multiplicity will be made.

Similar methods (described in Section 8.2.1) to compare treatment differences in quantitative and qualitative efficacy and exploratory outcomes will be employed.

Secondary analyses will be performed to assess the robustness of the conclusions and may include the use of a secondary analysis set (e.g., the Per Protocol population (PP) consisting of all subjects in the MITT population who did not have a major protocol violation), alternative methods to deal with missing data, and alternative methods to deal with potential violations of distribution assumptions for the primary analyses. Such sensitivity analyses will be outlined in the SAP for the study.

Additional exploratory analyses may be performed and will be defined and outlined in the SAP for the study.

9 STUDY MANAGEMENT

9.1 Compliance with protocol

The study shall be conducted as described in this approved protocol. The investigator should not implement any deviation or change to the protocol without prior review and documented approval/favorable opinion from the IRB of an amendment, except where necessary to eliminate an immediate hazard(s) to study participants.

If a deviation or change to a protocol is implemented to eliminate an immediate hazard(s) prior to obtaining IRB/ approval/favorable opinion, as soon as possible the deviation or change will be submitted to:

- IRB for review and approval
- Pfizer
- Regulatory Authority(ies), if required by local regulations

If an amendment substantially alters the study design or increases the potential risk to the participant: (1) the consent form must be revised and submitted to the IRB(s) for review and approval/favorable opinion; (2) the revised form must be used to obtain consent from participants currently enrolled in the study if they are affected by the amendment; and (3) the new form must be used to obtain consent from new participants prior to enrollment.

If the revision is an administrative letter, investigators must inform their IRB(s).

9.2 Record Retention

Source documents are original documents, data, and records from which the subject's case report form data are obtained. These include but are not limited to hospital records, clinical and office charts, laboratory and pharmacy records, diaries, imaging, and correspondence. All original source documents supporting entries in the case report forms must be maintained and be readily available.

The Investigator and the study center staff are responsible for maintaining a comprehensive and centralized filing system of all study-related (essential) documentation in accordance with Section 8 of the ICH Guidelines (E6), suitable for inspection at any time by representatives from the Sponsor or designee and/or applicable regulatory authorities. The clinical site's regulatory document binder essential elements should include:

- Subject files containing completed case report forms (eCRFs), informed consents/assents, and supporting copies of source documentation
- Study files containing the protocol with all amendments, Package Insert, copies of pre-study documentation and all correspondence to and from the IEC/IRB and the Sponsor or designee.
- If drug supplies are maintained at the study center, documentation for proof of receipt, study drug accountability records, return of study drug for destruction, final study drug product reconciliation statement, and all drug-related correspondence.

The investigator must retain all study records and source documents for the maximum period required by applicable regulations and guidelines, or institution procedures, whichever is longer.

9.3 Study Drug Record

It is the responsibility of the investigator to ensure that a current disposition record of investigational product is maintained at each study site where study drug is inventoried and dispensed. Records or logs must comply with applicable regulations and guidelines.

9.4 Study Drug Destruction

Study drugs are to be destroyed on site upon sponsor approval, it is the investigator's responsibility to ensure that arrangements have been made for disposal, and that procedures for proper disposal have been established according to applicable regulations, guidelines, and institutional procedures. Appropriate records of the disposal must be maintained.

9.5 Study Monitoring

Throughout the course of the study, data will be monitored for accuracy and completeness and study procedures will be monitored for adherence to the protocol and Good Clinical Practices (GCP). Clinical data monitoring will be conducted utilizing experienced clinical monitors. The monitoring plan includes routine remote monitoring with 1 annual site visit.

During the on-site visits, the CRFs will be reviewed for completeness and adherence to the protocol, accuracy, consistency of data, and adherence to local regulations on the conduct of clinical research.

A Medical Safety Monitor, a physician with clinical trials experience and expertise in scleroderma who is independent of the conduct of the study, will review all SAEs.

10 RESEARCH USE OF HUMAN SPECIMENS, SAMPLES, OR DATA

10.1 Use of Stored Samples and Data

Samples and data collection under this protocol may be used to study effect of tofacitinib on skin and blood gene expression and effect on T-cell biology. No genetic testing will be performed.

